3.1 Visit Schedule

Patients will have protocol-specified follow-up visits every six months (± 2 weeks) for three years. Visits will be timed from the date of randomization.

Additional visits may be scheduled as needed (see section 3.2).

3.2 Protocol Visits

3.2.1 Examination Procedures

Prior to the patient's examination by the investigator, the clinic coordinator will update the child's history, and will verify the spectacle prescription using a lensometer.

The following procedures will be performed without cycloplegia and by the same methods as were used at the enrollment visit:

1. Subjective refraction of both eyes

- The purpose of the subjective refraction is to determine whether the patient's spectacle prescription should be changed (see section 3.4.1).
 - If the investigator is changing the spectacle correction, the subsequent testing at this visit will be performed with the patient wearing the correction to be prescribed.

2. Oculomotor assessment using cover-uncover test and Alternate Prism and Cover Test (APCT) (see section 2.4.1)

- Both assessments should be performed as follows, without cycloplegia, using the specified correction in trial frames:
 - At distance and near, using the specified correction*
 - At near with +2.00D over the specified correction*

3. Measurement of accommodative response in the right eye by using Grand Seiko open field autorefractor

- Measurement will be taken with patient wearing trial frames with the specified correction* in front of the right eye and an occluder in front of the left eye.

*The specified correction is the patient's current correction unless the spectacle correction is being changed at this visit, in which case it is the new spectacle correction.

The protocols for the above examination procedures are described in the Testing Procedures Manual.

3.2.1.1 Additional Procedure at Annual Visits

At annual visits, cycloplegic autorefraction of both eyes will be performed using the Grand Seiko autorefractor after administration of 1% tropicamide.

503 Cycloplegic autorefraction should be performed after all other examination procedures have been
504 completed.

505

506 **3.2.2 Masking of Treatment Group**

507 At all visits, the investigator will be masked to the patient's treatment group. Patients will remove
508 their spectacles prior to the exam and will not wear the spectacles for any exam procedures.

509

510 **3.3 Additional Visits**

511 In order to maintain masking of the study investigator, any time the patient reports any type of
512 problem (e.g. blurry vision, headaches, etc.), a visit should be scheduled for an examination by
513 an unmasked consulting clinician.

514

515 The procedures and assessments to be completed for this examination are at the discretion of the
516 consulting clinician. A subjective refraction can be performed if the consulting clinician
517 suspects that the refractive error may not be optimally corrected. Other clinical procedures as
518 outlined in the protocol can be used to assess the nature of the problem and to arrive at a viable
519 treatment.

520

521 The patient's spectacle prescription may be changed if indicated (see section 3.4.1). On rare
522 occasions in which the patient's problem is not resolved by a change in spectacle prescription,
523 and the consulting clinician feels that a change in lens type (i.e. treatment crossover) may be
524 warranted, the consulting clinician should contact the protocol chair to discuss the case.
525 Prescribing a change in lens type will be permitted only with prior approval of the protocol chair.

526

527 **3.4 Treatment During Follow Up**

528 The patient should wear the random-assigned spectacles during all waking hours. Contact lenses
529 should not be worn.

530

531 Vision therapy may not be prescribed.

532

533 **3.4.1 Prescription Changes**

534 A prescription change must be made if the subjective refraction finding differs from the
535 current prescription by at least 0.50 D in spherical equivalent. Prescription changes can
536 be made for smaller differences at investigator discretion if the new prescription
537 improves the patient's visual acuity by at least one line over that in their current spectacle
538 correction. Whenever a spectacle change is made, spectacles will be prescribed according
539 to the endpoint of the subjective refraction (i.e. minimum minus for best acuity).

540

541 All prescription changes will be documented and tracked.

542

543 For progressive addition lenses, prescription changes apply to distance correction only; the power of
544 the addition will remain constant (i.e., +2.00D) throughout the study.

545
546
547
548
549
550
551
552
553
554
555
556
557
558
559
560
561
562
563
564
565
566
567
568
569
570
571
572
573
574
575
576
577
578
579
580
581
582
583
584
585
586
587
588
589

CHAPTER 4: MISCELLANEOUS CONSIDERATIONS IN FOLLOW-UP

4.1 Patient Withdrawals

A patient (and in this case the parents or guardians) may withdraw from the trial at any time. Based on the high retention (98.5% after 3 years) in COMET1, patient withdrawal is expected to be very infrequent. If the parents or guardians indicate that they want to withdraw the child from the study, the investigator personally should attempt to speak with them to determine the reason.

4.2 Discontinuation of Study

A patient who is found to be ineligible for the study or for whom there are substantial deviations from the protocol may be discontinued from the study. The patient may continue to receive necessary clinical care from the investigator or care may be transferred to another clinician with the consent of the parents.

The study may be discontinued by the Steering Committee (with approval of the Data and Safety Monitoring Committee) before all patients have completed the protocol-specified period of follow up.

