101 the accommodative response measured by the COMET2 method was 0.35 D less than by the
102 COMET method, meaning that the accommodative lag was greater by the same amount.

103 Therefore, COMET2 is very likely enrolling some patients with larger accommodative response
104 (i.e. less accommodative lag) than that of COMET patients in the subgroup which showed a
105 clinically meaningful treatment effect of PALs.
106

107 While the results of the pilot study support reducing the lower limit of accommodative response
108 to 2.15 D, it was decided to reduce the limit further to 2.00 D for two reasons. The first reason
109 relates to the future ability of clinicians in the community to implement the definition of high
110 accommodative lag, as clinicians normally measure accommodative response using monocular
111 estimation method (MEM) retinoscopy or Nott retinoscopy, the former of which measures
112 accommodative lag in quarter-diopter steps. Second, adopting a threshold of 2.00 D helps to
113 ensure that COMET2 will enroll children who truly have higher accommodative lags.
114

115 Impact of Change

116 Recruitment

117 Because sample size for the primary analysis was based on enrolling 100 patients, the study now
118 plans to recruit 100 patients whose accommodative response is in the range required under the
119 new threshold, up to a maximum of 150 patients total.

120

121 Informed Consent

122 No changes will be needed to the informed consent or assent documents.

123

124 Existing Randomized Patients Not Meeting Revised Criterion

125 Approximately 25% of the patients randomized thus far have accommodative response which
126 exceeds the revised criteria. The proposal is that such patients continue in the study, masked,
127 and in their assigned treatment groups. There is no reason to think that patients with less
128 accommodative lag wouldn't benefit from treatment, even though they might not be expected to
129 have the same degree of treatment benefit as would patients with higher amounts of lag. Also,
130 there are no unique safety concerns related to patients with lesser amounts of accommodative lag
131 wearing PALs, in fact, some clinicians prescribe PALs to similar patients in their routine
132 practices based solely on the presence of esophoria.

133

134 Although these patients will be able to continue in the study, given that they were consented into

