135 the study on the basis of their having certain characteristics including high accommodative lag, it
136 is felt that some form of disclosure is warranted. At the patient's next study visit, the
137 investigator will inform the patient and parent that the patient may not have as much difficulty
138 focusing (accommodating) as was previously thought. In addition to verbally conveying this
139 information, parents will be given a written IRB-approved disclosure statement. Parents and
140 patients will be encouraged to have the patient stay in the study but will have the option to
141 withdraw. Masking of treatment group will be maintained regardless of whether the patient
142 continues in the study or opts to withdraw.

143

144 Primary Analysis

145 The primary analysis will include data from all randomized patients, regardless of whether the
146 patient meets the revised accommodative response criterion.

147

148
149
150
151
152
153
154
155
156
157
158
159
160
161
162
163
164
165
166
167
168
169
170

CONTACT INFORMATION

COORDINATING CENTER

[name]., Ph.D. (Director)
Jaeb Center for Health Research
[name]
[name]
[contact]PEDIG or [contact]
[contact]PEDIG or [contact]

PROTOCOL CHAIR

[name].
The New England College of Optometry
[name]
[contact]

| | | |
|-----|----------------------------------------------------------------------|-----|
| 171 | CHAPTER 1: BACKGROUND AND SUMMARY | 1-1 |
| 172 | 1.1 Objective | 1-1 |
| 173 | 1.2 Rationale | 1-1 |
| 174 | 1.3 Synopsis of Study | 1-1 |
| 175 | 1.4 Study Screening/Enrollment Summary Flowchart | 1-3 |
| 176 | 1.5 Randomized Trial Summary Flowchart..... | 1-4 |
| 177 | CHAPTER 2: SCREENING/ENROLLMENT..... | 2-1 |
| 178 | 2.1 Eligibility Assessment and Informed Consent..... | 2-1 |
| 179 | 2.2 Screening..... | 2-1 |
| 180 | 2.2.1 Non-cycloplegic Procedures | 2-1 |
| 181 | 2.2.2 Eligibility for Screening with Cycloplegic Autorefraction..... | 2-2 |
| 182 | 2.2.3 Cycloplegic Autorefraction..... | 2-3 |
| 183 | 2.3 Randomization | 2-3 |
| 184 | 2.4 Prescribing Spectacles | 2-4 |
| 185 | 2.5 Obtaining Spectacles..... | 2-4 |
| 186 | CHAPTER 3: FOLLOW-UP | 3-1 |
| 187 | 3.1 Visit Schedule | 3-1 |
| 188 | 3.2 Protocol Visits..... | 3-1 |
| 189 | 3.2.1 Examination Procedures | 3-1 |
| 190 | 3.2.2 Masking of Treatment Group..... | 3-2 |
| 191 | 3.3 Additional Visits | 3-2 |
| 192 | 3.4 Treatment During Follow Up..... | 3-2 |
| 193 | 3.4.1 Prescription Changes | 3-2 |

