6.1 Sample Size Estimation

6.1.1 Randomized Trial

The sample size for the randomized trial has been estimated to be 50 patients per treatment group in order to have 90% power to detect at least a 0.60 D difference in myopia progression between treatment groups allowing for 10% loss to follow up. An adjustment for treatment group crossover was not made as this was very infrequent in COMET (2 out of 469 children) and is expected to be similarly infrequent in COMET2.

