6.2 Statistical Analysis

6.2.1 Randomized Trial

6.2.1.1 Primary Analysis

The primary analysis will be a comparison of the average change from baseline to 3 years in amount of myopia between children in the single-vision lens group and the children in the progressive-addition lens group.

The primary outcome is change from baseline to 3 years in spherical equivalent refractive error (SER) in diopters (D) as measured by cycloplegic autorefraction. For each eye, the Grand Seiko autorefractor will yield 5 readings consisting of sphere, cylinder, and axis. Each reading will be converted to a spherical equivalent refractive error (SER) and the median of the 5 SER values will be used for analysis.

The primary analysis will be a treatment group comparison of mean 3-year change in amount of myopia using the t-test. For each time point, the spherical equivalent refractive error (SER) values for a given child will be calculated using the average of the spherical equivalent refractive errors from each eye. Change in amount of myopia will be calculated as the difference of the child's SER at 3 years minus the child's SER at baseline.

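### Section 4.2 lets randomised children be discontinued for ineligibility or protocol deviations without keeping their 3-year measurement, so primary outcomes can be lost avoidably and possibly unevenly between arms

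*Protocol*

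**What the plan says.** Section 4.2 (Discontinuation of Study), in the chapter on follow-up, states that a patient "found to be ineligible for the study or for whom there are substantial deviations from the protocol may be discontinued from the study". It does not define a substantial deviation, does not say who decides, and is not limited to the period before randomisation or to safety. It goes on: "The patient may continue to receive necessary clinical care from the investigator or care may be transferred to another clinician". Neither this section nor any other provides for study visits or refraction after discontinuation.

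Amendment #2, under Primary Analysis, states: "The primary analysis will include data from all randomized patients". Section 6.2.1.1 defines the analysis: "The primary analysis will be a treatment group comparison of mean 3-year change in amount of myopia using the t-test". The change is the 3-year value minus the baseline value, both by cycloplegic autorefraction.

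On sample size, section 6.1.1 states: "The sample size for the randomized trial has been estimated to be 50 patients per treatment group". The target behind that number is a difference of 0.60 D with 90% power, and the allowance for losses is 10%.

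**The concern.** An analysis of all randomised children needs a 3-year refraction from as many of them as possible. Section 4.2 opens a study-initiated route by which that measurement is never taken, in addition to withdrawals by families.

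The two grounds differ in risk. Ineligibility concerns facts that predate assignment, so removal on that ground may well be unrelated to arm. Deviations come after assignment. Section 3.4 requires the assigned spectacles in all waking hours and bars contact lenses and vision therapy, so contact lens use or another departure from assigned wear could count as a deviation. Section 4.4 expects early difficulty with reading, steps and side vision for some children in progressive lenses, and section 6.2.1.2 plans to compare spectacle wear between the groups. The protocol thus allows that adherence may differ by lens type. If children removed for deviations also progress differently, the children left in the two arms are no longer comparable as randomised.

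**Working it through.** **1. Follow a discontinued child through the text.** Section 4.2 ends participation and mentions only care afterwards. Section 3.2.1.1 places cycloplegic autorefraction at annual study visits. A child discontinued before year 3 therefore has no 3-year value and no change score for the t-test in section 6.2.1.1. Refractions from year 1 or 2 may exist, but they are not the primary outcome. The statement in Amendment #2 about all randomised patients can be met in substance only if such children are still measured at 3 years, and nothing in the protocol arranges that.

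**2. Reproduce the sample size as far as possible.** Inputs from section 6.1.1: 50 per arm, 10% loss, 90% power, 0.60 D. Evaluable children: 50 × (1 − 0.10) = 45 per arm. The section gives no SD or alpha, so the sample size can only be solved backwards. Assuming two-sided 0.05:

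- Normal approximation: SD = 0.60 × √(45/2) / (1.960 + 1.282) = 0.878 D.
- t-test (noncentral t): SD = 0.868 D.

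Other assumptions give other values by the normal formula: 0.973 D at one-sided 0.05 and 0.738 D at two-sided 0.01. I use 0.868 D below.

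**3. Size of a possible bias.** Suppose a fraction f of one arm is removed, and those children's mean change differs by g from that of the children who remain. The full-arm mean is (1 − f) × rest + f × removed, so the mean of the remaining children is off by f × g. Neither f nor g is in the protocol. I take g = 1 SD = 0.868 D as a stress value. For f, 1.5% is the complement of the 98.5% retention that section 4.1 cites from the earlier trial. It is a rate of loss there, not a forecast of how often this rule would be used. The values 5% and 10% are assumptions.

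| f | Shift = f × 0.868 | Share of 0.60 D |
|---|---|---|
| 1.5% | 0.013 D | 2% |
| 5% | 0.043 D | 7% |
| 10% | 0.087 D | 14% |

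For scale, 10% of 50 is five children. With no true effect and 50 per arm before removal, a shift of 0.087 D in one arm raises the two-sided type I error from 5% to about 7.7% (SE = 0.868 × √(1/45 + 1/50) = 0.178 D; normal approximation). At 1.5% it stays at about 5.1%.

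**4. Power (noncentral t, SD 0.868 D, difference 0.60 D).**

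| Loss per arm | n per arm | Power |
|---|---|---|
| 10% (as planned) | 45 | 90.0% |
| 1.5% withdrawal + 5% removal | 46.75 | 91.1% |
| 1.5% withdrawal + 10% removal | 44.25 | 89.5% |
| 10% loss + 5% removal | 42.5 | 88.3% |
| 10% loss + 10% removal | 40 | 86.3% |

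Power falls noticeably only if the full 10% allowance is already spent on other losses, whereas section 4.1 expects withdrawal to be very rare.

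**The case against.** The rule is permissive: a child may be discontinued, not must be. It does not say that data already collected are discarded. Investigators are masked to treatment at all visits (section 3.2.2), and the unmasked consulting clinician sees children only for reported problems. Section 4.1 cites 98.5% retention and section 6.1.1 cites 2 crossovers in 469 children (0.4%) in the earlier trial, so heavy use of the rule is not expected. How missing 3-year values are handled is commonly left to the analysis plan. All of this stands, and it limits the likely size. It does not remove the point: an analysis plan can choose a method for missing values, but it cannot recover a refraction that was never taken.

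Three stronger readings are tempting, and the documents do not support them.

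- **That section 4.2 contradicts Amendment #2 on the children outside the revised accommodation criterion.** Those children met the criterion in force when they were randomised, and the amendment keeps them explicitly: "The proposal is that such patients continue in the study, masked". They are not children found ineligible in the sense of 4.2. The two texts cover different children.
- **That a change of lens type would trigger removal.** Section 3.3 allows such a change with the protocol chair's prior approval, so an approved change follows the protocol and is not a deviation.
- **That the trial loses material power, or that the primary analysis becomes a per-protocol comparison.** The power table shows little loss on the protocol's own retention figure. Removal related to arm and outcome is possible under 4.2, but nothing shows that it will happen.

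**Conclusion.** The point holds at moderate severity. Section 4.2 permits discontinuation of randomised children on loosely defined grounds and makes no provision for their 3-year cycloplegic refraction, which the all-randomised primary analysis needs. The resulting gaps are avoidable and, where they follow deviations, may be related to lens type.

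The size depends on how often the rule is used, which the protocol does not state: a shift of about 0.01 D in one arm's mean at 1.5% removal, and up to about 0.04 to 0.09 D at 5 to 10%. These figures assume a 1 SD difference between removed and remaining children, removal in one arm only, and an SD of about 0.87 D back-solved at two-sided 0.05. If the rule is rarely used, or used equally in both arms for similar children, the bias is negligible.

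**What to change.** Amend section 4.2 to say that ineligibility found after randomisation, or a protocol deviation, is recorded but does not by itself end data collection. Unless consent is withdrawn or the study is stopped, the scheduled visits continue to be sought, and at least the annual and 3-year cycloplegic autorefraction, whatever lenses the child is wearing. The child is analysed in the assigned group. The study-level stop in the same section is unaffected.

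This changes data collection and analysis only. It says nothing about which lenses or care a child should receive. The cost is one sentence and the continued running of visits that sections 3.1 and 3.2.1.1 already schedule.

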4.3 Risks of Examination Procedures

The procedures in this study are part of routine eye care in the United States and pose no known risks. As part of a routine usual-care exam, the patient may receive cycloplegic/dilating eye drops.

4.4 Risks of Treatment

Any type of spectacle wear has a minimal risk for injuries related to frames/lens breakage. Single-vision lenses are routinely prescribed for nearsighted children and pose no additional known risks. The risks of wearing progressive addition glasses are largely unknown. Some children may have some difficulty in the first week with reading, going down steps, and seeing things off to the side. It is not known whether wearing this type of glasses for a long period of time has an effect on accommodative response.

The risks of wearing either type of spectacles are the same as those that would be present wearing the given type of spectacles outside of the study.

4.5 Reporting of Adverse Events

1. A diagnosis of tropia, occurrence of double vision, and any injuries related to frames/lens breakage are to be recorded on the Follow-up Examination Form.
2. Each investigator is responsible for informing his/her IRB of serious treatment-related adverse events and abiding by any other reporting requirements specific to his/her IRB.
3. Data on the complications of study treatment will be tabulated regularly by the Coordinating Center for review by the Steering Committee. Serious complications will be reported expeditiously to the Data and Safety Monitoring Committee, which will receive a full adverse

590 event report semi-annually. Following each DSMC data review, a summary will be provided to
591 IRBs.

592

593 **4.6 Patient Payments**

594 Each patient screened for the study will be given a gift certificate valued at \$10, regardless of
595 their participation in the ancillary study or their eligibility for the randomized trial.

596

597 For patients who are eligible for the randomized trial and elect to participate, the following
598 payments will be made to the parent/guardian:

599

- \$25 for enrollment into the randomized trial
- \$25 for completion for each follow-up visit, up to a maximum of \$150

600

601

602 If there are extenuating circumstances, additional funds may be provided for travel if expenses
603 exceed \$25 and the patient will be unable to complete the visit without the reimbursement of the
604 travel expenses.

605

606 **4.7 Contacts by the Jaeb Center for Health Research**

607 The Jaeb Center serves as the PEDIG Coordinating Center. The Jaeb Center will be provided
608 with the parent/guardian's contact information. Contact information will be used for issuing
609 payments and for making phone contacts when necessary to facilitate visit scheduling. A patient
610 newsletter, study updates, and a study logo item may be sent. Patients will be provided with a
611 summary of the study results in a newsletter format after completion of the study by all patients.

612
613 **CHAPTER 5: MEM AND NOTT ACCOMMODATION ANCILLARY STUDY**

614
615 **5.1 Overview**

616 As part of screening to identify patients eligible for the randomized trial, patients at participating
617 centers will be asked to participate in an ancillary study consisting of testing of accommodative
618 response by MEM and Nott retinoscopy before completing the screening measurement of
619 accommodative response by Grand Seiko autorefraction. Recruitment for the ancillary study
620 will continue as part of screening for the randomized trial until 300 patients have been enrolled
621 into the ancillary study.

622
623 Patients do not need to participate in the MEM and Nott accommodation study in order to enter
624 the randomized trial. Also, many patients in the MEM and Nott accommodation study will not
625 be eligible for the randomized trial and will end their study participation with the initial visit.

626
627 Consent for this ancillary study is covered in the informed consent for screening for the
628 randomized trial.

629
630 **5.2 Objectives**

631 The objectives of the study are to compare the following measurements of accommodative
632 response obtained by the following methods:

- 633 • Monocular Estimate Method (MEM) retinoscopy vs. Grand Seiko autorefractor
- 634 • Nott retinoscopy vs. Grand Seiko autorefractor
- 635 • Monocular Estimate Method (MEM) retinoscopy vs. Nott retinoscopy

636
637 **5.3 Rationale**

638 If the randomized trial finds that progressive-addition lenses (PALs) slow myopia progression to
639 a clinically significant degree in children with reduced accommodative response, a new
640 challenge will arise in clinical practice: how to identify such children as candidates for treatment
641 with PALs.

642
643 Little data are available on the accuracy of the two clinical techniques that are used by some
644 practitioners to measure accommodative response: Monocular Estimation Method (MEM)
645 retinoscopy and Nott retinoscopy. Autorefractors such as the Grand Seiko open-field
646 autorefractor provide an objective measurement of accommodative response but these
647 instruments are available in few practices due to their high cost. Thus, the current ancillary study
648 is being undertaken to compare data obtained using clinical measures of accommodative
649 response--MEM and Nott retinoscopy--to objective measurements obtained with the Grand Seiko
650 autorefractor.

651
652 The aim is to help determine whether a simple, effective measure exists that can be easily used
653 by clinicians to identify children with reduced accommodative response who, if they have low
654 myopia and esophoria, might benefit from treatment with PALs.

655
656 **5.4 Background**

657 The fundamental strategy in both the MEM and Nott retinoscopy techniques is to provide a
658 subject with a near target (e.g. words at a distance of 33 cm) that is viewed binocularly.

659 Retinoscopy is then used to determine how closely the subject's accommodative response
660 approximates the accommodative demand created by the target, and, to determine the amount of
661 under-accommodation (lag) or over-accommodation (lead).

662
663 In the Monocular Estimate Method (MEM),⁶ the reading target is mounted on the retinoscope
664 and has a hole through which retinoscopy is performed. Spherical lenses are introduced briefly in
665 front of one eye to neutralize the perceived motion. This technique assumes that accommodative
666 response is maintained by the other eye while the lenses are introduced and that the lenses are
667 introduced for no more than 300 msec, less than the latency of the accommodative response.

668
669 In Nott retinoscopy, the reading target is held at a fixed distance and the clinician performs the
670 retinoscopy slightly off-axis, moving the retinoscope closer to, or farther from the subject to
671 neutralize the reflex. The amount of accommodative response is calculated from the distance at
672 which the neutral motion occurs and is interpreted with regard to the accommodative demand
673 created by the target.

674
675 MEM retinoscopy is more commonly referenced in the literature than Nott retinoscopy, and may
676 be simpler to perform because the distance of the target/retinoscope from the subject is fixed.
677 However, the examiner must be sure that the lenses are inserted and removed very quickly so as
678 not to alter the accommodative response. In adults, Nott retinoscopy has been reported to have
679 higher inter-observer agreement⁷ and to provide higher values of accommodative lag than MEM
680 retinoscopy.⁸

681 682 **5.5 Eligibility Criteria**

683 The eligibility criteria are the same as for the randomized trial except for the following:

- 684 • Eligibility criterion for amount of myopia is refractive error in the range of -0.50D to -
685 3.00D spherical equivalent by subjective refraction.
- 686 • There is no eligibility criterion related to the amount of accommodative response, as the
687 study aims to test children with a wide range of accommodative responses.
- 688 • There is no eligibility criterion related to presence of and/or amount of esophoria

689 690 **5.6 Procedures**

691 The MEM measurements and the Nott retinoscopy measurements must be taken by different
692 study-certified examiners, with each examiner masked to the measurements taken by the other
693 examiner.

694
695 The testing will be performed without cycloplegia and prior to the measurement of
696 accommodative response using the Grand Seiko autorefractor. Accommodative response should
697 be measured in the right eye three times using MEM retinoscopy and three times using Nott
698 retinoscopy. For a given patient, the procedure (MEM or Nott retinoscopy) to be performed first
699 will be randomized. The randomly-assigned testing order for each patient will be specified on a
700 log sheet which the Coordinating Center will generate for each site.

701
702 The protocols for MEM and Nott testing are described in the Testing Procedures Manual.

CHAPTER 6: SAMPLE SIZE AND STATISTICAL ANALYSIS

The estimation of sample size and statistical analysis plan are summarized below and detailed in separate documents.

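### Section 4.5 names breakage as the only injury to record on the follow-up form, so non-serious injuries with intact spectacles and the PAL difficulties listed in 4.4 have no prescribed record

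*Protocol*

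**What the plan says.** Protocol section 4.5 has three items.

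- **Item 1** fixes the content of the form: tropia, double vision, and "any injuries related to frames/lens breakage are to be recorded on the Follow-up Examination Form".
- **Item 2** makes each investigator "responsible for informing his/her IRB of serious treatment-related adverse events".
- **Item 3** has the Coordinating Center tabulate complications of study treatment. Serious complications go promptly to the DSMC, which also receives a full adverse event report every six months.

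Section 4.4, just before it, describes the risks. On breakage: "Any type of spectacle wear has a minimal risk for injuries related to frames/lens breakage". On the test lenses: "The risks of wearing progressive addition glasses are largely unknown", and "Some children may have some difficulty in the first week with reading, going down steps, and seeing things off to the side". It does not mention falls or fall injuries.

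Section 3.2.2 states that at all visits "the investigator will be masked to the patient's treatment group". Section 3.3 sends a child who reports any problem to an unmasked consulting clinician and leaves the assessments to that clinician's discretion. Section 3.2.1 has the coordinator update the child's history before each protocol examination.

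**The concern.** The risk section and the recording section do not line up. The one injury category named for the form is the one that 4.4 attributes to spectacles of every type. Section 2.5 adds that both lens types are polycarbonate, so the protocol gives no reason to expect breakage injuries to differ between arms. The difficulties that 4.4 ties to PALs, including going down steps and seeing to the side, have no item on the named list, and neither does an injury that might follow from them while the spectacles stay intact.

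The children are 8 to under 12 years old, and section 3.4 asks them to wear the assigned spectacles throughout their waking hours for three years. If sites follow item 1 as written, a table with no excess of injuries under PALs could reflect what was asked rather than what happened. What is recorded at the visit is settled by the protocol and its forms. An analysis plan cannot recover data that were never collected.

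**Working it through.** The protocol states no figure on this point, so there is none to reproduce. The check is mainly a comparison of sections.

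**Step 1. Match each risk in 4.4 to a record in 4.5.**

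| Risk in 4.4 | Applies to | Named in 4.5 item 1? |
|---|---|---|
| Injury from frame or lens breakage | Any spectacles | Yes |
| Difficulty with reading, first week | PALs | No |
| Difficulty going down steps, first week | PALs | No |
| Difficulty seeing to the side, first week | PALs | No |
| Effect of long wear on accommodation | PALs | No, but accommodative response is measured at every protocol visit (3.2.1) |

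**Step 2. Trace an injury with intact spectacles, for example a fall, through the other routes.**

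- *Serious and judged treatment-related:* reported to the IRB under item 2 and, as a serious complication, to the DSMC under item 3. This route is open.
- *Not serious:* item 2 does not apply. Item 3 tabulates complications, but the only form content that 4.5 specifies is the item 1 list.
- *Problem visit under 3.3:* the family must first report a problem. Procedures are discretionary, and no adverse event record is named.
- *History update under 3.2.1:* no injury question is specified.

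The non-serious injury therefore has no prescribed record.

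**Step 3. Timing.** Section 2.5 encourages collection of the spectacles within 2 weeks of randomization, so the first week of wear ends about 1 to 3 weeks after randomization. The first protocol visit is at six months (about 26 weeks) ± 2 weeks, that is, weeks 24 to 28 (3.1). The gap is 24 − 3 = 21 to 28 − 1 = 27 weeks. Unprompted recall of a first-week event would be weak.

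**Step 4. What recording could show (illustration only).** Section 6.1.1 gives n = 50 per arm. Allowing 10% loss leaves 45, and the maximum of 150 patients in Amendment 2 gives 75. The injury rates below are assumptions, because the documents give none.

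- Upper one-sided 95% limit when no events are seen, 1 − 0.05^(1/n): 5.8% at n = 50, 6.4% at n = 45, 3.9% at n = 75.
- Chance of at least one event among 50, 1 − (1 − p)^50: 64% at p = 2%, 92% at p = 5%, over 99% at p = 10%.
- Power to compare arms at two-sided 0.05, Φ{[|p2 − p1| − 1.96·√(2p̄(1 − p̄)/n)] / √[(p1(1 − p1) + p2(1 − p2))/n]} with n = 50 and p̄ the mean of p1 and p2: 13% for 2% versus 5%, 39% for 2% versus 10%, 83% for 2% versus 20%.

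Recording would probably show whether such injuries occur at rates of a few percent. Only a large difference between lens types could be tested.

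**The case against.** The strongest reply is that item 1 is a list of required entries and does not exclude others, while item 3 speaks of complications in general and of a full adverse event report. The Follow-up Examination Form is not at hand and may have a general field. All of this is fair. What stands is narrower: the protocol names no place for these events, and a full report can contain only what sites were told to collect.

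A reader might infer that fall injuries as a class drop out of the safety data. The documents do not support that, because a serious fall judged treatment-related goes to the IRB and the DSMC. That judgement is harder for an investigator who does not know the lens type, but the consulting clinician under 3.3 is unmasked and can help where the family reports a problem.

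A reader might also infer that the protocol says PALs cause falls. It says only that some children may have difficulty in the first week. The step from that to an injury is plausible, but it is the reader's own. Nor does section 6.2 describe a formal safety comparison from which falls could be missing. It describes twice-yearly DSMC reports, and a comparison may stand in the separate analysis document.

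Finally, asking about all injuries for three years would collect ordinary childhood accidents and could dilute a short early effect. That is a real cost. It is a reason to record timing, not a reason to leave the item as it is.

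**Conclusion.** The point holds in limited form. Breakage is the only injury category that 4.5 item 1 names for the form, and it is the risk that 4.4 assigns to all spectacles. Non-serious injuries without breakage, and the adaptation difficulties that 4.4 names for PALs, have no prescribed record, so the tabulated data and DSMC reports may miss them.

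The number of events missed cannot be derived from the documents. At an assumed 2% to 10% rate of such injuries, 50 × 0.02 = 1 to 50 × 0.10 = 5 children per arm would be affected. How many of those would go unrecorded depends on how many were serious and on what the unseen form contains.

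The conclusion rests on sites recording what 4.5 tells them to and on the form having no broader injury field. If it has one, the protocol text still needs to say so. The primary outcome and its analysis are untouched. This is a minor point with a cheap remedy.

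**What to change.** Reconcile 4.4 and 4.5 by rewording item 1 so that the form records:

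1. tropia and double vision, as now;
2. any injury since the last visit, including falls, whatever the cause, with frame or lens breakage as a sub-item;
3. any difficulty with reading, going down steps or seeing to the side;
4. for each entry under 2 and 3, the time since the spectacles were dispensed or last changed.

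Ask the questions in the same words in both arms at every protocol visit and at 3.3 consulting visits, and show the answers by arm in the DSMC report. The coordinator, who already updates the history before the examination, could ask them, so that an answer about steps or side vision does not hint at lens type to the masked investigator.

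The cost is a few fields on an existing form, a matching record for consulting visits, and some lines in the DSMC tables. Ordinary childhood injuries will be recorded in both arms, and recall of first-week events at six months will be imperfect, although the timing field helps to separate early events. With about 50 children per arm the results should be presented as descriptive, with confidence limits and no test-based claim of equal safety.
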